## **11.8 Additional Assessments**

PK and PD parameters will be summarized using descriptive statistics: number of subjects, mean, median, SD, minimum, maximum, and coefficient of variation, geometric mean and geometric mean SD.

### **11.8.1 PK Assessments**

Plasma concentrations will be summarized using descriptive statistics. Mean and individual subject vadadustat concentrations and O-glucuronide (primary metabolite of vadadustat) concentrations will be plotted versus time on linear and semi-logarithmic axes. The following PK parameters for vadadustat and O-glucuronide will be estimated as deemed appropriate from the plasma concentrations using standard methods of non-compartmental analyses:  $C_{max}$ ,  $T_{max}$ ,  $AUC_{last}$ ,  $AUC_{inf}$ , elimination rate constant ( $\lambda z$ ), and  $t_{1/2}$ .  $CL/F$  and  $V_d/F$  will be estimated for vadadustat. PK analysis will be reported separately.

### **11.8.2 PD Assessments**

A by-subject listing of all PD variables will be provided including the changes from Baseline/Day 1. The observed and change from Baseline/Day 1 values of all PD assessments will be summarized using descriptive statistics. An exposure-response analysis of vadadustat, EPO and other PD measures will be conducted as deemed appropriate. PD analysis may be reported separately.

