Inclusion Criteria	
Subjects must meet the following inclusion criteria:
 
 
1. ≥18 years of age
 
2. Receiving chronic, outpatient in-center hemodialysis (TIW) for end-stage renal disease for at least 12 weeks prior to Screening
 
3. Maintained on IV epoetin alfa therapy for 8 weeks prior to and including Screening through SV2
 
4. Eligibility in the Main study and ESA hyporesponder parallel study is based on the following mean weekly epoetin alfa doses: 
 
• Main study: Mean weekly epoetin alfa dose <300 U/kg/week for 8 weeks prior to SV2
 
• ESA hyporesponder parallel study: Mean weekly epoetin alfa dose ≥300 U/kg/week for 8 weeks prior to SV2
 
 
 
5. Two Hb values measured by the central laboratory at least 4 days apart between SV1 and SV2 as indicated below: 
 
• Main study: 2 Hb values between 8.5 and 11.0 g/dL, inclusive
 
• ESA hyporesponder parallel study: 2 Hb values between 8.0 and 10.0 g/dL, inclusive
 
 
 
6. Serum ferritin ≥100 ng/mL and transferrin saturation (TSAT) ≥20% during Screening
 

	

7. Folate and vitamin B12 measurements <math>\geq</math> lower limit of normal during Screening

8. Hemodialysis adequacy as indicated by single-pool Kt/Vurea <math>\geq</math>1.2 using the most recent historical measurement within 8 weeks prior to or during Screening

9. Understands the procedures and requirements of the study and provides written informed consent and authorization for protected health information disclosure.

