concentration-time curve (AUC) and maximum concentration ( $C_{max}$ ) in Phase 1 and Phase 2 studies covering the dose range of 80 to 1200 mg after single administration and 500 to 900 mg after repeated daily administration for 10 days. The plasma half-life of vadadustat was about 4 to 6 hours, 7 to 8 hours, and 9 to 10 hours in healthy subjects, NDD-CKD patients, and DD-CKD patients, respectively.

Vadadustat is extensively metabolized and its metabolites are eliminated from the body by dual routes of excretion (both renal and fecal). The urinary excretion of vadadustat and its metabolites has been shown to be less than 60% in healthy human volunteers. In a clinical study conducted to evaluate the effect of hemodialysis on the exposures to vadadustat, hemodialysis did not have an effect on the exposures of vadadustat or its metabolites. Given its short half-life and the dual routes of elimination, vadadustat is unlikely to accumulate in patients with CKD.

Multiple doses of 700 and 900 mg daily for up to 10 days (Study AKB-6548-CI-0002 [CI-0002]) and single doses of 1200 mg (Study AKB-6548-CI-0001 [CI-0001], Study AKB-6548-CI-0010 [CI-0010]) have been examined in healthy volunteers. Vadadustat demonstrated dose-proportional PK and achieved serum EPO concentrations up to 34.4 mIU/mL, levels considered physiologic and below exposures achieved with injectable ESAs ([Besarb 1992](#)). A higher incidence of adverse events (AEs) in the gastrointestinal System Organ Class (SOC) – nausea, diarrhea, abdominal pain, dyspepsia – was observed in groups treated with 700, 900, or 1200 mg compared with lower vadadustat doses or placebo. Most AEs were mild to moderate, short-lived (1 or 2 days), and assessed as unrelated by investigators. No AEs led to study withdrawal, and no serious adverse events (SAEs) were reported. No clinically meaningful changes or abnormalities in vital signs, safety laboratory studies, or electrocardiogram (ECG) parameters were reported.

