### 6.1.1 Screening Period (up to 28 days; Day -28 to Baseline/Day 1)

For all subjects (Main study and ESA hyporesponder parallel study), the Screening Period starts at the time the informed consent is signed and will be a maximum of 28 days in duration. Baseline/Day 1 will be performed within 28 days of the start of Screening. Subjects who meet all eligibility criteria will be randomized to a vadadustat treatment arm or an epoetin alfa treatment arm. Subjects will be required to stop epoetin alfa treatment for a minimum duration of 5 days before Baseline/Day 1 in the Main study and for a minimum of 2 days before Baseline/Day 1 in the ESA hyporesponder parallel study. In the Main study, randomization will

be stratified by the mean weekly epoetin dose calculated over a period of 8 weeks prior to Screening Visit 2 (SV2):

- Low epoetin alfa dose group ( $\leq 90$  U/kg/week) or
- High epoetin alfa dose group ( $> 90$  to  $< 300$  U/kg/week)

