### 7.2 Inclusion Criteria

Subjects must meet the following inclusion criteria:

1.  $\geq 18$  years of age
2. Receiving chronic, outpatient in-center hemodialysis (TIW) for ESRD for at least 12 weeks prior to Screening
3. Maintained on IV epoetin alfa therapy for 8 weeks prior to and including Screening through SV2
4. Eligibility in the Main study and ESA hyporesponder parallel study is based on the following mean weekly epoetin alfa doses:
  - Main study: Mean weekly epoetin alfa dose  $< 300$  U/kg/week for 8 weeks prior to SV2
  - ESA hyporesponder parallel study: Mean weekly epoetin alfa dose  $\geq 300$  U/kg/week for 8 weeks prior to SV2
5. Two Hb values measured by the central laboratory at least 4 days apart between SV1 and SV2 as indicated below:
  - Main study: 2 Hb values between 8.5 and 11.0 g/dL, inclusive
  - ESA hyporesponder parallel study: 2 Hb values between 8.0 and 10.0 g/dL, inclusive
6. Serum ferritin  $\geq 100$  ng/mL and transferrin saturation (TSAT)  $\geq 20\%$  during Screening
7. Folate and vitamin B12 measurements  $\geq$  lower limit of normal during Screening
8. Hemodialysis adequacy as indicated by single-pool Kt/Vurea  $\geq 1.2$  using the most recent historical measurement within 8 weeks prior to or during Screening
9. Understands the procedures and requirements of the study and provides written informed consent and authorization for protected health information disclosure.

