#### **9.2.2.1 PK/PD Sampling for Subjects Randomized to Vadadustat**

Refer to [Appendix B](#) for a schematic overview of the PK/PD samples for the vadadustat arm.

Blood for measurement of vadadustat, metabolites and EPO level in the vadadustat arm, in both the Main study and ESA hyporesponder parallel study, will be collected as outlined below. Preferably, PK/PD samples are to be taken on the day of hemodialysis after the first short interdialytic interval (e.g., at the second session of the week).

At Baseline/Day 1, PK/PD samples will be collected prior to dialysis and administration of vadadustat.

At Week 1 (after at least a full week of vadadustat treatment), vadadustat will be administered between 15 minutes to one hour prior to the start of dialysis. Blood samples will be collected as follows:

- 15 minutes pre-dose, and 2 hours  $\pm$  15 minutes, 3.5 hours  $\pm$  15 minutes and 5 hours  $\pm$  30 minutes post-dose
- From subjects enrolled at a subset of study sites only, additional samples will be collected at 7 hours  $\pm$  30 minutes and 10.5 hours  $\pm$  1.5 hours post-dose

On the following non-dialysis day, blood samples will be collected as follows:

- 15 minutes pre-dose, and 2 hours  $\pm$  15 minutes, 3.5 hours  $\pm$  15 minutes, and 5 hours  $\pm$  30 minutes post-dose
- From subjects enrolled at a subset of study sites only, additional samples will be collected at 7 hours  $\pm$  30 minutes post-dose

At Week 11, vadadustat will be administered between 15 minutes to one hour prior to the start of dialysis. Blood samples will be collected as follows:

- 15 minutes pre-dose, and 2 hours  $\pm$  15 minutes, 3.5 hours  $\pm$  15 minutes, and 5 hours  $\pm$  30 minutes post-dose
- From subjects enrolled at a subset of study sites only, additional samples will be collected at 7 hours  $\pm$  30 minutes and 10.5 hours  $\pm$  1.5 hours post-dose

At Week 13 (after at least one week on TIW vadarustat dosing regimen), vadarustat will be administered between 15 minutes to one hour prior to the start of dialysis. Blood samples will be collected as follows:

- 15 minutes pre-dose, and 2 hours  $\pm$  15 minutes, 3.5 hours  $\pm$  15 minutes, and 5 hours  $\pm$  30 minutes post-dose
- From subjects enrolled at a subset of study sites only, additional samples will be collected at 7 hours  $\pm$  30 minutes and 10.5 hours  $\pm$  1.5 hours post-dose

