### 9.3.1 Screening Visits

Subjects will need to sign a full consent form prior to SV1 procedures. The consent form may be signed in advance of the SV1 procedures. The Screening Period starts at the time the informed consent is signed and will be a maximum of 28-days in duration. Two Screening visits (SV1 and SV2, with a minimum of 4 days in between) must be performed within the Screening Period and prior to dosing (Baseline/Day 1).

A subject may enter the washout period only after all eligibility criteria have been met following SV2. During the washout period, no epoetin alfa will be administered before Baseline/Day 1 for 5 days in the Main study and 2 days in the ESA hyporesponder parallel study.

After obtaining informed consent, subjects will undergo a number of Screening activities.

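### In the ESA hyporesponder study, the within-arm change from Baseline/Day 1 in EPO can include residual injected epoetin and be biased downward

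*Protocol*

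**What the plan says.** Five parts of the current protocol text meet here.

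- **Prior treatment.** Section 7.2 requires that subjects be "Maintained on IV epoetin alfa therapy for 8 weeks prior to and including Screening through SV2". The synopsis sets the dose: "ESA hyporesponder parallel study: Mean weekly epoetin alfa dose ≥300 U/kg/week for 8 weeks prior to SV2".
- **Washout.** Section 6.1.1 requires epoetin to be stopped "for a minimum of 2 days before Baseline/Day 1 in the ESA hyporesponder parallel study". Section 9.3.1 puts it as "no epoetin alfa will be administered before Baseline/Day 1 for 5 days in the Main study and 2 days in the ESA hyporesponder parallel study".
- **Sampling.** Section 9.2.2.1 has EPO drawn in the vadadustat arm at Baseline/Day 1, before dialysis and the first dose. On the choice of day it says: "Preferably, PK/PD samples are to be taken on the day of hemodialysis after the first short interdialytic interval". Section 9.2.2.2 uses the same term, EPO level, for the measurement in the epoetin arm. One of that arm's samples is taken before the dose on the next dialysis day, which Appendix B labels Week 1 + 2 days.
- **Endpoint.** Section 5.4 lists EPO first among the PD parameters.
- **Analysis.** Section 11.8.2: "The observed and change from Baseline/Day 1 values of all PD assessments will be summarized using descriptive statistics". It makes no exception for EPO or for the hyporesponder study.

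**The concern.** On three-times-weekly dialysis, the short gap between sessions is about 2 days. A hyporesponder dosed at every session could receive a full dose at one session and give the Day 1 sample at the next without missing a dose. If the assay reads injected epoetin as EPO, the baseline is the subject's own EPO plus whatever is left of that dose. Subtracting it from a later value pulls the change down by the leftover amount.

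This is not a detail left open for the SAP. The protocol itself fixes both the short interval and the change score, and its own epoetin-arm schedule samples injected epoetin at the same 2-day distance from a dose. At stake is how the EPO response is read within the hyporesponder vadadustat arm, about 15 subjects. A small or negative mean change there could reflect carry-over rather than a weak response.

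**Working it through.** The protocol states no power, precision or effect figure for EPO, so there is no planned figure to reproduce. The check is how much injected epoetin could remain in the Day 1 sample.

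**Inputs from the protocol**
- Weekly dose at the entry threshold: 300 U/kg. Over three sessions, 300 ÷ 3 = 100 U/kg per dose (this assumes three-times-weekly dosing; higher weekly doses give more).
- Shortest interval to baseline: 2 days = 48 h. For comparison, the Main study's 5 days = 120 h.
- Week 1 profile after at least 7 days of vadadustat: 2 + 7 = 9 days = 216 h since the last epoetin dose.
- Highest EPO concentration quoted for vadadustat: 34.4 mIU/mL (Sections 4.2 and 6.3).

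**Assumptions not in the protocol**
- Epoetin half-life 4 to 13 h; distribution volume V = 50 mL/kg, varied from 40 to 100; endogenous EPO 10 mIU/mL; an assay that reads injected epoetin as EPO.

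**Residual at baseline.** With one-compartment decay after an IV bolus,

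residual(t) = (dose ÷ V) × 2^(−t ÷ half-life).

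At V = 50 mL/kg the starting concentration is 100 ÷ 50 = 2 U/mL = 2000 mIU/mL.

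**Effect on the change score.** For illustration, take an on-drug value of 34.4 and an endogenous baseline of 10, so the true change is 34.4 − 10 = +24.4. The change read is 24.4 − residual.

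| Half-life (h) | Residual at 48 h (mIU/mL) | Change read, 48 h gap | Residual at 120 h (mIU/mL) | Change read, 120 h gap |
|---|---|---|---|---|
| 4 | 0.5 | +23.9 | 0.0 | +24.4 |
| 5 | 2.6 | +21.8 | 0.0 | +24.4 |
| 6 | 7.8 | +16.6 | 0.0 | +24.4 |
| 8 | 31.3 | −6.9 | 0.1 | +24.3 |
| 10 | 71.8 | −47.4 | 0.5 | +23.9 |
| 13 | 154.7 | −130.3 | 3.3 | +21.1 |

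**Thresholds at 48 h.** The residual equals the assumed endogenous level of 10 when half-life = 48 ÷ log2(2000 ÷ 10) = 6.3 h (6.0 to 7.2 h for V from 40 to 100 mL/kg). It equals the illustrative rise, so the sign turns, when half-life = 48 ÷ log2(2000 ÷ 24.4) = 7.5 h (7.2 to 9.0 h over the same volumes).

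**Other intervals.** At 72 h the residual is at most 43 mIU/mL for V = 50 (54 for V = 40). At 216 h it is at most 0.02, so Week 1 values on vadadustat are in effect free of the pre-study epoetin.

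**Between the randomized arms.** Let b be mean endogenous baseline and r the mean residual, equal in both arms in expectation because the washout precedes randomized treatment. The difference in mean change is (on-treatment mean, vadadustat − b − r) − (on-treatment mean, epoetin − b − r). Both b and r drop out. What remains is extra variance, because r differs between subjects and there are only about 15 per arm.

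**The case against.** Most of the case against limits the point rather than removing it.

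- **Observed EPO is already summarized.** True: the sentence in 11.8.2 covers observed values as well as changes, and subject listings are planned. The post-baseline information is therefore not lost. The change score is still prescribed alongside it without a caution.
- **The size rests on outside assumptions.** This stands. Over V from 40 to 100 mL/kg, the 48 h residual runs from 0.2 to 193 mIU/mL. A reader might infer that the change score will hide vadadustat's effect; the documents support only that it can.
- **34.4 mIU/mL is not a response.** Correct. Section 4.2 reports healthy volunteers who "achieved serum EPO concentrations up to 34.4 mIU/mL, levels considered physiologic", in text on 700, 900 and 1200 mg. It is an absolute concentration, not a change and not a hemodialysis value, and serves here only as a yardstick.
- **Two days may not be the usual gap.** Section 6.1.1 makes it a minimum, and the second-session timing is a preference. If Section 9.3.1 means two full epoetin-free days, a Monday dose would rule out a Wednesday Day 1. The last dose would then be the previous Friday, about 120 h earlier, with a residual of at most about 4 mIU/mL. The wording allows either reading, so the short gap is possible but not shown to be typical.
- **Stronger consequences are not planned analyses.** A reader might infer a false difference between hyporesponders and the Main study, but the synopsis says the two are analysed separately. A reader might also infer a biased exposure-response analysis, but 11.8.2 leaves that to judgement and does not name change from Day 1 as its response. Nor is the randomized comparison of changes biased in expectation.

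**Conclusion.** The point holds as a limited one. In the hyporesponder study, the prescribed within-arm change from Baseline/Day 1 in EPO uses a baseline that may follow IV epoetin by only 2 days, so it can be biased downward. The bias is negligible if the epoetin half-life is 4 to 5 h and material from about 6 h. Above about 7 to 9 h it could reverse the sign of a rise of the illustrated size. These figures rest on the assumed dose per session, volume, half-life, endogenous level and assay behaviour; the protocol can confirm only the weekly dose threshold and the 2-day minimum.

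Post-baseline observed EPO is sound, and so in expectation is the between-arm difference in change, at some cost in variance. EPO is one of several PD measures in an exploratory, descriptive study, and no test or decision depends on this summary. It is a cheap improvement, not a flaw in the trial's conclusions.

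**What to change.** Add to Section 11.8.2, for EPO in the ESA hyporesponder study, wording to this effect:

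> For EPO in both treatment arms of the ESA hyporesponder parallel study, the main summaries are the observed values and the rise from the pre-dose sample of the same visit (Week 1 in both arms; also Weeks 11 and 13 for vadadustat where sampled). Change from Baseline/Day 1 is secondary, is presented for both arms by time since the last pre-study epoetin dose, and is not used alone to judge the size of the EPO response.

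Everything needed is already collected: the pre-dose samples under Sections 9.2.2.1 and 9.2.2.2, and at least 8 weeks of ESA history under Section 9.2.1. Both arms should be handled alike. Dropping the change score in the vadadustat arm only would discard the comparison in which the bias cancels.

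The cost is a few lines of text and one extra grouping variable. The drawback is that a same-visit pre-dose value is taken on treatment, so it shows the rise per dose, not the change from an untreated state. The point calls for no change to the washout. It also gives no ground for omitting EPO samples after ESA rescue: without a defined window, that would remove post-randomization data by an unstated rule.

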### **11.8.3 Concomitant Medications**

Prior and concomitant medications will be coded using World Health Organization Drug dictionary. Refer to [Section 8.5](#), Prior and Concomitant Therapy.

### **11.8.4 Biomarkers**

Biomarkers (including, but not limited to, hepcidin and VEGF) will be summarized descriptively at Baseline/Day 1 and by visit post-Baseline/Day 1.

## 12 DATA HANDLING AND RECORD KEEPING

### 12.1 CRFs/EDC

This study will utilize an EDC system to manage data collection during this trial. The system is fully Code of Federal Regulations 21 part 11 compliant. An EDC system contains certain functionality including, but not limited to, a graphical user interface to help facilitate data entry, a data validation element to check user data, and a reporting function. CRFs available through this system are required and will be completed for each randomized subject.

Any form of data from the electronic system are the sole property of the sponsor and will not be made available in any form to third parties, except for authorized representatives of the sponsor or appropriate regulatory authorities, without written permission from the sponsor.

The investigator has ultimate responsibility for the accuracy, authenticity, and timely collection and reporting of all clinical, safety, and laboratory data entered in the EDC or any other data collection forms. The CRFs will be signed electronically by the investigator to attest that the data contained on the CRFs is true.

In most cases, the source documents are contained in the subject's chart at the hospital or the physician's office. In these cases, data collected on the CRFs will match the data in those charts.

### 12.2 Record Retention

To enable evaluations and/or audits from regulatory authorities or the sponsor, the investigator agrees to keep records, including the identity of all participating subjects (sufficient information to link records, e.g., CRFs and hospital records), all original signed informed consent forms, copies of all CRFs, SAE forms, source documents, detailed records of drug disposition, and adequate documentation of relevant correspondence (e.g., letters, meeting minutes, and telephone calls reports). The records will be retained by the investigator according to the International Council for Harmonisation of Technical Requirements for Pharmaceuticals for Human Use (ICH), local regulations, or as specified in the Clinical Study Agreement, whichever is longer.

If the investigator becomes unable for any reason to continue to retain study records for the required period (e.g., retirement and relocation), the sponsor will be prospectively notified. The study records will be transferred to a designee acceptable to the sponsor, such as another investigator, another institution, or to the sponsor. The investigator will obtain sponsor's written permission before disposing of any records, even if retention requirements have been met.

## 13 QUALITY CONTROL AND QUALITY ASSURANCE

### 13.1 Study Site Monitoring Visits

During study conduct, the sponsor or its agent will conduct periodic monitoring visits to ensure that the protocol and Good Clinical Practice (GCP) are being followed. The monitors will review source documents to confirm that the data recorded on the CRFs is accurate. The investigator/institution will allow the sponsor's monitors or designees and appropriate regulatory authorities direct access to source documents to perform this verification.

The study site may also be subject to Quality Assurance audits performed by the sponsor or companies working with or on behalf of the sponsor, and/or review by the IRB, and/or to inspection by appropriate regulatory authorities.

It is important that the investigator(s) and their relevant personnel are available during the monitoring visits and possible audits or inspections and that sufficient time is devoted to the process.

### 13.2 Protocol Deviations

A protocol deviation is generally an unplanned excursion from the protocol that is not implemented or intended as a systematic change. The investigator is responsible for ensuring the study is conducted in accordance with the procedures and evaluations described in this protocol and must protect the rights, safety, and welfare of subjects. The investigator should not implement any deviation from, or changes of, the protocol, unless it is necessary to eliminate an immediate hazard to trial subjects.

A protocol waiver is a documented prospective approval of a request from an investigator to deviate from the protocol. Protocol waivers are strictly prohibited.

For the purposes of this protocol, deviations requiring notification to sponsor are defined as any subject who:

- Entered into the study even though they did not satisfy entry criteria.
- Developed withdrawal criteria during the study and not withdrawn.
- Received wrong treatment or incorrect dose.
- Received excluded concomitant treatment.

When a deviation from the protocol is identified for an individual subject, the investigator or designee must ensure the sponsor is notified. The sponsor will follow-up with the investigator, as applicable, to assess the deviation and the possible impact to the safety and/or efficacy of the subject to determine subject continuation in the study.

If a deviation impacts the safety of a subject, the investigator must contact the sponsor immediately.

The investigator will also assure that deviations meeting IRB/IEC and applicable regulatory authorities' criteria are documented and communicated appropriately. All documentation and communications to the IRB/IEC and applicable regulatory authorities will be provided to the sponsor and maintained within the Trial Master File.

**Note:** Other deviations outside of the categories defined above that are required to be reported by the IRB/IEC in accordance with local requirements will be reported, as applicable.

